The participants will be randomized to treatment with sealed therapeutic shoe or TCC. The randomization will be stratified for ulcer size (smaller or bigger than 1 cm^2 , ulcer size calculated as longest diameter*longest perpendicular diameter) and study center, and use random permuted blocks of randomly varying size.

Recruitment of participants

People who fulfill the inclusion criteria and not the exclusion criteria will be given oral and written study information and asked about whether they are interested in participating in the study. Those who agree will sign an informed constant to participate.

Intervention group, sealed therapeutic shoe: A prosthetist/orthotist will try out new therapeutic shoes to the participants and make individual insoles after casts of the feet. There will a limited number of shoe types to choose between and the procedure and material for the insole production will be standardized. The ulcer will be offloaded by adjusting the insoles with the help of plantar pressure measurement using the F-scan system (Tekscan, Boston, MA, USA). The “seal” of the shoe consists of a soft plastic strip (Bracelok, DJO Nordic, Malmö) that have to be broken to remove the shoe.

[figure not shown]
Control group, TCC: The participants will be treated with TCC, applied in a standardized manner. Participants in this group will also receive shoes and insoles, according to the same protocol as above, before TCC treatment is initiated to be comparable to the other group in the long-term follow-up after healing, when both groups will use shoes and insoles to prevent reulceration.

Both groups will visit the cast technician 1-2 times/per week depending on the status of the ulcer. The cast technician will change dressings, note whether the seal has been broken (for the intervention group), change casts (for the control group), photograph and document ulcers and complications, and ask participants if they have experienced any issues with the treatment. After this, a new dressing is applied, and the shoe is sealed (intervention group) or

a new cast is applied (control group). Participants will use a cover on the shoe or cast while taking a shower, and for the intervention group a cover will also be used when sleeping. Both groups will receive written information about potential complications and contact information to the clinics.

Data collection

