Participants in both groups will be assessed by a physiotherapist on five occasions (Figure 1): at base-line, four weeks into the treatment period, and then 1, 6 and 12 months after healing (when treatment is ended). For the 4 week into treatment and 1 month post-treatment assessments, a visit window of ± 1 week will be used. For the 6 and 12 months post-treatment assessments, a visit window of ± 1 month will be used. Standardized and validated instruments and assessment methods will be used for the data collection (Table 1).

Aim 1: Ulcer healing (primary end point)

Primary outcome measure is ulcer healing after 12 weeks of treatment, defined by the Food and Drug Administration (FDA) as full skin epithelization of the ulcer, confirmed by a second observation 14 days later.¹⁸ The cast technicians will assess ulcer healing in both the intervention group and control group. They will also photograph the ulcer and healed skin so a person blinded to group allocation can assess ulcer healing afterwards.

Aim 2: Adverse events during treatment (secondary end points)

Adverse events that are judged to be related to the offloading devices (shoe or TCC) will be classified as adverse device effects (ADE) and serious adverse device effects (SADE).³² ADE include, but are not limited to, skin abrasions, blisters, sleep disturbances, issues with gait and balance, etc. SADE include, but are not limited to, new foot ulcers that result in amputation (major amputation = above ankle, minor amputation = below ankle), sepsis, etc.

Adverse events that are not related to the offloading devices are classified as adverse events (AE) and serious adverse events (SAE).³² AE include, but are not limited to, skin abrasions, new foot ulcers on the contralateral foot and not related to the device, etc. SAE include, but are not limited to, death, amputation, onset of acute Charcot foot, sepsis, etc. (not related to the offloading device). However, in accordance with previous studies on this patient population, the investigators choose not to include all AE and SAE as the patient population suffers from multiple co-morbidities and therefore a high incidence of illness and hospital admissions unrelated to the DFU and offloading devices can be expected.³³ Therefore, all

ADE and SADE will be assessed, but only certain types of AE and SAE that are of particular interest, such as, amputation, death and onset of acute Charcot foot.

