ADE, SADE, AE and SAE will be assessed with the aid of questionnaires, case report form (CRF), photographs of ulcer and skin, and patient files.

Aim 3: Long-term effects (secondary end points)

The secondary endpoints are time to healing and measures listed in Table 1. Each secondary endpoint is measured between one and five occasions during the study. For example, incidence of new foot ulcers, amputation, onset of acute Charcot-foot, death, adherence to using therapeutic shoes and locus of control will be assessed. Our hope is that the positive experience in the intervention group of that using therapeutic shoes can heal ulcers will result in a stronger internal locus of control and higher adherence to using therapeutic shoes after healing, so that fewer people will reulcerate or be affected by foot complications in the long term.

Data from patient files, questionnaires and the physiotherapists' assessments will be used for the analysis.

Aim 4: Health-economic outcomes (secondary end points)

The questionnaires RAND-36 and EQ-5D-5L will be used to assess general quality of life. Data from patient journals, Swedish Social Insurance Agency's system, and self-report questionnaires will be used to assess health care consumption and other costs.

Statistical analysis

See separate document for statistical analysis plan.

Research ethics

The participants will be informed about risks of the interventions in the written information that also will include contact information for the clinics. Risks will be minimized by excluding certain patient groups with heightened risks of side-effects not being noted or reported, and by a frequent follow-up during the intervention period. The study has been approved by the region ethics review board in Uppsala, Sweden (documents 2018/387 and 2019-03512).

Table 1. Overview of variables and assessment methods.

Variable	Assessment method	Assessment occasion					Specific aim
		Treatment period		Follow-up after treatment end			
		Base-line	4 weeks	1 month	6 months	12 months	
Ulcer healing	Clinical observation + blinded photo assessment	X	X	X			1
Skin complications	Clinical observation + blinded photo assessment	X	X	X			2
Glycemic control	Blood sample (HbA1c) ^a	X	X	X	X	X	2,3
BMI	Measurement of weight and height	X	X	X	X	X	2,3
Gait function	10 meter walk test ^{b 19}	X	X	X	X	X	2,3
Gait function	Timed up and go ^{b 20}	X	X	X	X	X	2,3
Balance	Berg balance scale ^{b 21}	X	X	X	X	X	2,3

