2.7 TIMING OF OUTCOME ASSESSMENTS

Table 1 below lists outcomes and time points for assessments (base-line, 4 weeks into treatment, and 1, 6 and 12 months after treatment end). For the 4 week into treatment and 1 month post-treatment assessments, a visit window of ± 1 week will be used. For the 6 and 12 months post-treatment assessments, a visit window of ± 1 month will be used.

Table 1. Overview of variables and assessment methods.

Variable (scale level: nominal=N, ordinal=O, interval=I)	Assessment method	Assessment occasion				
		Treatment period		Follow-up after treatment end		
		Base- line	4 weeks	1 month	6 months	12 months
Ulcer healing (N)	Clinical observation + blinded photo	X	X	X		
Skin complications (N)	Clinical observation + blinded photo	X	X	X		
Glycemic control (I)	Blood sample (HbA1c) ^a	X	X	X	X	X
BMI (I)	Measurement of weight and height	X	X	X	X	X
Gait function (I)	10 meter walk test ^{b 17}	X	X	X	X	X
Gait function (I)	Timed up and go ^{b 18}	X	X	X	X	X
Balance (O)	Berg balance scale ^{b 19}	X	X	X	X	X
Muscle atrophy (I)	Calf circumference ^{a 20}	X	X	X	X	X
General quality of life (O)	RAND-36 ^{c 21} , EQ-5D-5L ^{c 22}	X	X	X	X	X
Disease-specific quality of life (O)	DFS-SF ^{c 23}	X	X	X	X	X
Physical activity (I)	ActivPAL ^{d 24}	X	X	X	X	X
Physical activity (O)	National Board of Health and Welfare's indicator questions ²⁵	X	X	X	X	X
Bone mass density (I)	DXA ^e (heel bone)	X		X	X	X
Locus of control (O)	Questions from MHLC-C ^{c 26}	X		X	X	X
Ankle range of motion (I)	Goniometer ^{a 27}	X		X	X	X
Ankle strength (I)	Dynamometer ^{a 28}	X		X	X	X
Adherence to therapeutic shoes (O)	Questions from Q-TFA ^{c 29}	X		X	X	X
Treatment satisfaction (O)	Visual analogue scale ^c		X	X		
New ulcers, amputations, death, Charcot foot (N)	Patient file and self-report ^c				X	X
Health care consumption (O) ^f	Patient administration systems and self-report ^c			X	X	X
Sick leave from work (I) ^f	Self-report, ^c Swedish Social Insurance Agency's system			X	X	X

^aStandardized method, ^bfunction test, ^cquestionnaire, ^dactivity monitor, ^eDual-energy X-ray absorptiometry ^ffor the of health-economic analysis.

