3 STATISTICAL PRINCIPLES

3.1 CONFIDENCE INTERVALS AND P VALUES

In all analyses a 95% confidence level will be used as a cut off to declare statistical significance, and report both exact p-values and 95% CI. One-sided tests and CI will be used for the primary outcome and two-sided tests and CI the secondary outcomes. No adjustment for multiple comparisons will be used.

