5.2 EFFICACY ASSESSMENTS

5.2.1 PRIMARY EFFICACY ENDPOINT

Primary efficacy endpoint is ulcer healing at 12 weeks, defined as complete epithelialization which is maintained for a minimum of 14 days (as required by the US Food and Drug Administration, FDA)³¹. Ulcer healing will be assessed by the cast technician at the local hospital who redress the DFU, approximately 1-2 times per week (depending on the status of the DFU) in both groups. The cast technician will also photograph the DFU so it can be assessed by another person, blinded to group allocation.

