6 STATISTICAL ANALYSES

6.1 ANALYSIS METHODS

6.1.1 ANALYSIS OF THE PRIMARY EFFICACY ENDPOINT(S)

Primary efficacy endpoint is ulcer healing at 12 weeks, defined as complete epithelialization which is maintained for a minimum of 14 days (as required by the FDA).³¹ Healing is thus a single endpoint assessed on a nominal scale.

Ulcer healing will be assessed by the cast technician at the local hospital who redress the DFU, approximately 1-2 times per week (depending on the status of the DFU) in both groups. The cast technician will also photograph the DFU so it can be assessed by another person, blinded to group allocation.

In the analysis of the primary endpoint, the ITT dataset (analyzed with and without adjustment for covariates) and the per protocol dataset (analyzed without adjustment for covariates only) will be used. For the non-adjusted analyses, crude risk ratio (RR) or OR will be calculated to assess the impact of offloading device type on ulcer healing. For the adjusted analysis, baseline variables (sex, age, education level, living conditions, diabetes type and duration, glycemic control, BMI, history of previous foot ulcers and amputations, foot deformities, index foot ulcer characteristics, number of active ulcers, use of tobacco, peripheral artery disease, and neuropathy, see point 5.1) will be included as candidates in a logistic multiple regression, using backward selection and a p-value of 0.10 as cut-off for removal.

Participants for whom the 12 week observation is missing will be categorized as “not healed”. The statistician conducting the analysis will be blinded to group allocation.

The proportion of healed ulcers in each study group will be calculated, and the results will be presented as RR or OR and corresponding 95% CI.

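### The plan does not say whether the unblinded technician's call or the blinded photo read defines primary healing, and no listed analysis uses the blinded read

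*SAP*

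**What the plan says.** **Who assesses.** SAP 6.1.1 states: "Ulcer healing will be assessed by the cast technician at the local hospital who redress the DFU". SAP 5.2.1 and the protocol (Aim 1) agree. In the protocol's Methods, the paragraph on visits to the cast technician gives that same person the tasks of checking and renewing the shoe's seal or replacing the cast. The technician therefore cannot be blind to the arm.

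**The blinded read.** SAP 5.2.1 and 6.1.1 add: "The cast technician will also photograph the DFU so it can be assessed by another person, blinded to group allocation". The protocol's version is: "They will also photograph the ulcer and healed skin so a person blinded to group allocation can assess ulcer healing afterwards". Both make a blinded read possible. Neither names its timing, its procedure or its place in the analysis.

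**The tables.** For ulcer healing, Table 1 of the protocol gives the method as "Clinical observation + blinded photo assessment", and Table 1 in SAP 2.7 as "Clinical observation + blinded photo". Both sources are listed, without a rule for combining them.

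**The endpoint.** Healing is "defined as complete epithelialization which is maintained for a minimum of 14 days" (SAP 5.2.1). No independent confirmer is named.

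**The analyses.** SAP 6.1.1 and 6.1.8 plan intention-to-treat, per-protocol, covariate-adjusted and multiple-imputation analyses of the primary outcome. None of them varies the assessor. In the analysis, only the statistician is stated to be blinded.

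**The concern.** Complete closure is a visual judgement, and in an open-label device trial the person making it knows which device the patient wears. Blinding the statistician does not help once the ulcer has been classified by someone who was not blind.

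Two things are at stake. First, if the technician's call is used, a handful of borderline ulcers read differently by arm can move the estimated difference by several points against a limit of 10. Leniency toward the shoe would favour a false claim of non-inferiority. Severity toward it could hide a true one. Second, with two reads of the same endpoint and no ranking between them, the choice can be made after both results are known.

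**Working it through.** **The plan's own figure.** The documents give no figure for reading error. The only related figure is the sample size in SAP 2.3: 112 in total, 56 per group. The usual two-sample formula gives n per arm = (0.9×0.1 + 0.9×0.1) × (1.645 + 0.842)² / 0.10² = 111.3, so 112 per arm and not in total. That is a separate matter. Here 56 per arm (the stated minimum) and 75 per arm (half of the 150 target) are taken as the sizes the plan would deliver.

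**Inputs from the documents**
- Limit of 10%, read as 10 percentage points; expected healing 90% in both arms (SAP 2.3).
- Level: "In all analyses a 95% confidence level will be used as a cut off to declare statistical significance", one-sided for the primary outcome (SAP 3.1).

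**Assumptions**
- Non-inferiority is judged by a Wald bound on the risk difference. SAP 6.1.1 reports a risk or odds ratio and states no test against the limit.
- For false claims, true healing sits at the limit: shoe 80%, cast 90%.
- L is the share of truly unhealed ulcers called healed.

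**Rule.** With observed proportions s (shoe) and c (cast), non-inferiority is claimed if

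s − c − 1.645 × √[s(1−s)/n + c(1−c)/n] > −0.10.

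The probability of a claim is the sum, over all pairs of counts that satisfy the rule, of the product of the two binomial probabilities.

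**Observed rates after misreading**
- Leniency to the shoe only: 0.80 + 0.20L, giving 0.82 (L = 10%) or 0.85 (L = 25%). The apparent difference becomes −8 or −5 points.
- Leniency to the cast only: 0.90 + 0.10L, giving 0.91 or 0.925.
- Severity toward the shoe when both arms truly heal at 90%: 5% of healed shoe ulcers called unhealed gives 0.90 × 0.95 = 0.855.

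**Results, exact, 56 per arm**

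| Truth (shoe/cast) | Misreading | Probability of claiming non-inferiority |
|---|---|---|
| 80/90 | none | 0.0566 |
| 80/90 | shoe only, L = 10% | 0.1001 |
| 80/90 | shoe only, L = 25% | 0.2135 |
| 80/90 | cast only, L = 10% | 0.042 |
| 80/90 | cast only, L = 25% | 0.025 |
| 80/90 | both arms, L = 10% | 0.077 |
| 80/90 | both arms, L = 25% | 0.124 |
| 90/90 | none | 0.56 |
| 90/90 | 5% of healed shoe ulcers called unhealed | 0.24 |

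At 75 per arm, leniency to the shoe only gives 0.0563 (none), 0.1094 (L = 10%) and 0.2555 (L = 25%).

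**Check by normal approximation.** At 56 per arm and L = 10%, the standard error is √[(0.82×0.18 + 0.90×0.10)/56] = 0.065. The probability is Φ(0.02/0.065 − 1.645) ≈ 0.09, against 0.10 exact.

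**In patients.** At 80% healing, 0.20 × 56 = 11.2 shoe ulcers are truly unhealed. L = 10% is then about one ulcer and L = 25% about three.

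**The case against.** A reader might infer that the plan hands the endpoint to the unblinded technician, that bias-free reads already exist unused, and that leniency toward the shoe will pass straight into a false claim. The documents do not support that reading, for these reasons.

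- Table 1 in both documents makes the blinded photo part of the listed method for healing. The deciding read is undefined; it is not assigned to the technician.
- Photographs are planned, but the blinded read is only made possible. A blinded read is also not free of error. Equal leniency of 10% in both arms still gives 7.7% false non-inferiority at 56 per arm, against 10.0% when the shoe alone benefits. Blinding removes only the differential part.
- Nothing in the documents shows the direction or size of any bias. The shoe was developed by the trial's investigators, but the assessors are technicians at local hospitals, and nothing says they took part in developing it.
- The 14-day confirmation may catch some false closures, and the calculation gives it no credit. It is only a partial filter, since the same technician may make the second observation.

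These points narrow the concern. They do not supply a ranking of the two reads, a rule for disagreement or an analysis of the blinded read.

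**Conclusion.** The gap is real and should be closed. The plan foresees two reads of its primary endpoint, one of them unblinded, and leaves open which one counts. As written, the conclusion can rest on the unblinded call with nothing planned to test it.

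Under the stated assumptions, misreading one to three shoe ulcers in 56 as healed takes false non-inferiority from about 6% to 10–21%. At 75 per arm it goes from about 6% to about 11% (L = 10%) or 26% (L = 25%). Errors the other way are also costly: with equal true healing, the chance of showing non-inferiority falls from 56% to 24% at 56 per arm.

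These figures show how sensitive the result would be; they do not estimate bias in this trial. They depend on assumed misreading rates, on a risk-difference Wald test that the SAP does not specify, and on no errors being filtered at 14 days.

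**What to change.** In SAP 5.2.1 and 6.1.1 and in the protocol under Aim 1, state that the blinded photo read, at first closure and again at the 14-day confirmation, defines primary healing. Fix this before any read is analysed, including for the interim analysis in SAP 2.5, which uses the same outcome.

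Add pre-set rules for disagreement between the reads and for unreadable photographs. The second rule matters for two reasons. SAP 6.1.1 counts a missing 12-week observation as not healed, and it is unclear whether an unreadable photograph would fall under that. Falling back on the technician, on the other hand, readmits the unblinded judgement exactly where photographs fail.

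Add to SAP 6.1.8 the technician-based result as a sensitivity analysis, with agreement between the reads and counts of unreadable photographs by arm.

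**Cost.** The photographs and a blinded reader are already foreseen, so most of this is wording in two documents. A readable photograph must be ensured at both time points, and Table 1 schedules none explicitly for the 14-day check. Some photographs will be unreadable, and a photograph shows less than direct inspection.

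**Limit.** Treatment ends at healing, apparently on the technician's call. A later blinded read cannot undo that.

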5.2.2 SECONDARY EFFICACY ENDPOINTS

Secondary outcome measures (variables and assessment methods) are listed in Table 1. The cast technician will document and take photographs of skin complications. A physiotherapist will perform the standardized assessments (calf circumference, etc.) and function tests (gait, balance, etc.).

5.2.3 ADDITIONAL EFFICACY ENDPOINTS

Not applicable.

5.3 SAFETY ASSESSMENTS

5.3.1 ADVERSE EVENTS

Adverse events that are judged to be related to the offloading devices (shoe or TCC) will be classified as adverse device effects (ADE) and serious adverse device effects (SADE).³² ADE include, but are not limited to, skin abrasions, blisters, sleep disturbances, issues with gait and balance, etc. SADE include, but are not limited to, new foot ulcers that result in amputation (major amputation = above ankle, minor amputation = below ankle), sepsis, etc.

Averse events that are not related to the offloading devices are classified as adverse events (AE) and serious adverse events (SAE).³² AE include, but are not limited to, skin abrasions or new foot ulcers on the contralateral foot and not related to the device, etc. SAE include, but are not limited to, death, amputation, onset of acute Charcot foot, sepsis, etc. (not related to the offloading device). However, in accordance with previous studies on similar patient populations, not all AE and SAE will be included as the patient population suffers from multiple co-morbidities and therefore a high incidence of illness and hospital admissions unrelated to the DFU and offloading devices can be expected.³³ Therefore, all ADE and SADE will be assessed, but only certain types of AE and SAE that are of particular interest, such as, amputation, death and onset of acute Charcot foot.

ADE, SADE, AE and SAE will be assessed with the aid of questionnaires, CRF, photographs of ulcer and skin, and patient files.

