1.2 HYPOTHESES AND OBJECTIVES

The overarching objective is to evaluate whether sealed shoe can heal DFU at least as effectively as TCC, but with fewer adverse events during the treatment period, better long-term effects and to a lower cost.

Specific objectives

Objective 1. To investigate whether a sealed shoe can heal DFUs at least as effectively as TCC (non-inferiority, one-sided hypothesis testing).

Objective 2. To investigate whether there is a difference in adverse events during the treatment period with sealed shoe and TCC (superiority, two-sided hypothesis testing).

Objective 3. To investigate whether there is a difference in long-term effects (up to 12 months after end of treatment) with sealed shoe and TCC (superiority, two-sided hypothesis testing).

Objective 4. To investigate whether there is a difference in health economic outcomes between treatment with sealed shoe and TCC (superiority, two-sided hypothesis testing).

The null hypotheses are that a sealed therapeutic shoe does not heal DFUs at effectively as TCC, and that there are no differences between sealed shoe and TCC in side-effects, long-term effects and health economic outcomes.

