6.1.5 SUB-GROUP ANALYSES

There is some debate whether non-removable offloading devices (such as TCC) are effective and safe to use for people with peripheral artery disease and infected DFU. For this reason, sub-group analyses will

be conducted for people with impaired circulation and more infected DFU at baseline, for the primary outcome (healing) and adverse events.

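### For several kinds of foot event and for sepsis, a judgement of device-relatedness with no stated judge, criteria or blinding can decide whether the event is counted in the between-arm adverse-event comparison.

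*SAP*

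**What the plan says.** SAP 5.3.1 sorts events by cause. Those judged related to the shoe or the cast are adverse device effects (ADE), or serious ones (SADE). The rest are AE or SAE. The section then limits what is taken forward: "Therefore, all ADE and SADE will be assessed, but only certain types of AE and SAE that are of particular interest". Amputation, death and acute Charcot foot follow as examples of such types. The reason given is that "not all AE and SAE will be included as the patient population suffers from multiple co-morbidities", so much illness and many admissions unrelated to ulcer or device are expected. The protocol's Aim 2 text has the same rule: "ADE and SADE will be assessed, but only certain types of AE and SAE that are of particular interest".

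SAP 1.2 makes Objective 2 a two-sided superiority question, "whether there is a difference in adverse events during the treatment period with sealed shoe and TCC". SAP 6.1.3 compares the proportions in the categories AE, SAE, ADE and SADE by Chi-square test. SAP 6.1.5 adds sub-group analyses of adverse events, because "There is some debate whether non-removable offloading devices (such as TCC) are effective and safe to use for people with peripheral artery disease" and for infected ulcers.

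On who sees what, the protocol's description of the treatment visits says: "The cast technician will change dressings, note whether the seal has been broken (for the intervention group), change casts (for the control group"). The same technician photographs and documents ulcers and complications and asks about problems with the treatment. SAP 5.3.1 names questionnaires, CRF, photographs and patient files as sources. Neither document says who decides whether an event is device-related.

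**The concern.** If every event were collected, moving one from ADE to AE would change its label and it would still appear in another row of the same table. Under this rule an event judged unrelated leaves the table altogether unless its type is one of those kept. The relatedness judgement then acts as an entry criterion for the outcome.

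The arms look and feel different, and anyone who handles the device knows which it is. The background sections attribute most side-effects of TCC to immobilising the ankle joint, so views about which events a cast or a shoe can cause exist before the first participant is enrolled. If those views lead to different attribution of similar events, the Objective 2 test compares attribution as well as harm.

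The kept types are also left open. Types of unrelated event could be added, or not, after data have been seen.

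**Working it through.** **1. Which events does the rule leave to judgement?** Setting the examples in SAP 5.3.1 side by side:

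| Event | Example of a related event | Example of an unrelated event | Among the unrelated types named as kept |
|---|---|---|---|
| Skin abrasion | yes (ADE) | yes (AE) | no |
| Sepsis | yes (SADE) | yes (SAE) | no |
| New contralateral ulcer | no | yes (AE) | no |
| Amputation | yes (SADE, after a new ulcer) | yes (SAE) | yes |
| Acute Charcot foot | no | yes (SAE) | yes |
| Death | no | yes (SAE) | yes |

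The last three rows are safe, since they count whichever way they are judged. For the first three, a verdict of related brings the event in and a verdict of unrelated leaves its status undetermined. Falls and infection of the index ulcer are not mentioned in either list and are undetermined in the same way.

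**2. How much could it matter?** The documents give no adverse-event rate, no attribution rate and no power for Objective 2, so there is no plan figure to reproduce. The inputs from the plan are the group sizes (112/2 = 56 and 150/2 = 75 per arm, SAP 2.1 and 2.3), the two-sided 5% level (SAP 3.1) and the Chi-square test (SAP 6.1.3). Everything else is assumed.

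Let *p* be the true proportion of participants with at least one event of the exposed kinds, and *q* the probability that the event is judged related in a given arm. If unrelated events of these kinds are not counted, then

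counted proportion = *p* × *q*.

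The rejection probability is exact, by enumerating two independent binomials and applying the uncorrected Chi-square test.

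*False difference.* True rate 30% in both arms:

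| Attribution, one arm v the other | Counted proportions | Rejects, 56 per arm | Rejects, 75 per arm |
|---|---|---|---|
| 80% v 80% | 0.30 × 0.8 = 24% v 24% | 5.1% | 4.9% |
| 80% v 70% | 24% v 0.30 × 0.7 = 21% | 6.8% | 7.2% |
| 70% v 50% | 21% v 0.30 × 0.5 = 15% | 13.3% | 16.1% |
| 80% v 40% | 24% v 0.30 × 0.4 = 12% | 38.7% | 49.1% |

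*Hidden difference.* True rates 60% v 40%, all events counted: power is 56% at 56 per arm and 71% at 75. With attribution 60% v 90%, both counted proportions become 36% (0.60 × 0.6 and 0.40 × 0.9), and rejection falls to about 5%. With 70% v 90% they are 42% and 36%, and rejection is about 10% and 12%.

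The first row of the table shows that incomplete attribution alone does not inflate the error. The inflation comes from a gap between the arms.

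**3. A limit of this model.** It applies attribution once per participant. A participant with two exposed events is counted if either is judged related. With independent judgements, 80% v 40% per event becomes 1 − 0.2² = 96% v 1 − 0.6² = 64% per participant, so the gap narrows from 40 to 32 points.

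**The case against.** The filter is disclosed and reasoned. In a population this ill, collecting every unrelated event would add much noise. Four further points can be made for the plan, and most of them stand.

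- A reader might infer that unblinded staff make the relatedness judgement. The documents do not say so. They name no judge at all. What they support is that the staff who document complications know the arm and that no blinded step is stated for relatedness.
- A reader might infer that unrelated events are never recorded, so that nothing can be repaired later. The documents speak of events being assessed and included, and the protocol has complications documented at each visit with no causality condition. Some raw data on unrelated foot events may therefore exist. No analysis of them is planned.
- A reader might take all of Aim 2 to be affected. It is not. In the protocol's Table 1, skin complications (with blinded photo assessment), gait, balance and quality of life also serve Aim 2 and carry no attribution condition. They do not count falls or sepsis, however.
- A reader might expect the bias to favour the shoe, or the 6.1.5 analysis to be empty of the events it is about. Neither follows. One list of ADE examples serves both devices, and a new device may draw more attribution than a familiar one. Amputation, death, acute Charcot foot and all ADE and SADE remain available to the sub-group analysis.

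The stated reason for the filter does not reach the events at issue. It concerns illness unrelated to the ulcer and the device, which is no ground for dropping new foot lesions or infection of the index ulcer.

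**Conclusion.** The concern holds for the adverse-event comparison in SAP 6.1.3 and the adverse-event part of 6.1.5, and no further. For skin abrasions, contralateral ulcers, sepsis and similar events, the relatedness judgement can decide whether the event counts. The plan gives that judgement no owner, criteria or blinding, and leaves the kept types open.

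The size depends wholly on an attribution gap that the documents do not report. At a 30% true rate in both arms, a ten-point gap is nearly harmless (about 7% against a nominal 5%), a gap of 70% v 50% gives 13-16%, and a twofold gap gives 39-49%. These figures assume that unrelated events of the exposed kinds go uncounted and that attribution acts once per participant. A gap in the opposite direction to a true difference can remove most of the power to see it. The direction of any bias cannot be known from the documents. The change is worth making because it is cheap and must be settled before the data are seen.

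**What to change.** Keep the exemption for general illness unrelated to the ulcer or device.

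- **SAP 5.3.1 and protocol Aim 2:** replace the illustrative wording with a closed list of foot, limb and mobility events, counted in both arms whatever the causality judgement: skin lesion or new ulcer on either foot, infection of the index ulcer, sepsis, fall or fracture, amputation, acute Charcot foot, death.
- **SAP 6.1.3 and 6.1.5:** add the between-arm comparison of participants with at least one listed event regardless of cause, and read the Aim 2 adverse-event conclusion from it. Report ADE and SADE as the attributed subset.
- **SAP 5.3.1:** state who judges relatedness and by what criteria, with blinded assessment where feasible.

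The cost is a few more CRF fields at the existing visits (1-2 per week), slightly more event recording, and changes of wording in the two documents. No extra visits are needed.
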